## 12.2 Disease Parameters

Measurable disease. Measurable lesions are defined as those that can be accurately measured in at least one dimension (longest diameter to be recorded) as  $\geq 20$  mm by chest x-ray, as  $\geq 10$  mm with CT scan, or  $\geq 10$  mm with calipers by clinical exam. All tumor measurements must be recorded in millimeters (or decimal fractions of centimeters).

Note: Tumor lesions that are situated in a previously irradiated area will not be considered measurable unless progression is documented or a biopsy is obtained to confirm persistence at least 90 days following completion of radiation therapy.

Malignant lymph nodes. To be considered pathologically enlarged and measurable, a lymph node must be  $\geq 15$  mm in short axis when assessed by CT scan (CT scan slice thickness recommended to be no greater than 5 mm). At baseline and in follow-up, only the short axis will be measured and followed.

Non-measurable disease. All other lesions (or sites of disease), including small lesions (longest diameter  $< 10$  mm or pathological lymph nodes with  $\geq 10$  to  $< 15$  mm short axis), are considered non-measurable disease. Bone lesions, leptomeningeal disease, ascites, pleural/pericardial effusions, lymphangitis cutis/pulmonitis, inflammatory breast disease, and abdominal masses (not followed by CT or MRI), are considered as non-measurable.

Note: Cystic lesions that meet the criteria for radiographically defined simple cysts should not be considered as malignant lesions (neither measurable nor non-measurable) since they are, by definition, simple cysts.

'Cystic lesions' thought to represent cystic metastases can be considered as measurable lesions, if they meet the definition of measurability described above. However, if non-cystic lesions are present in the same patient, these are preferred for selection as target lesions.

Target lesions. All measurable lesions up to a maximum of 2 lesions per organ and 5 lesions in total, representative of all involved organs, should be identified as **target lesions** and recorded and measured at baseline. Target lesions should be selected on the basis of their size (lesions with the longest diameter), be representative of all involved organs, but in addition should be those that lend themselves to reproducible repeated measurements. It may be the case that, on occasion, the largest lesion does not lend itself to reproducible measurement in which circumstance the next largest lesion which can be measured reproducibly should be selected. A sum of the diameters (longest for non-nodal lesions, short axis for nodal lesions) for all target lesions will be calculated and reported as the baseline sum diameters. If lymph nodes are to be included in the sum, then only the short axis is added into the sum. The baseline sum diameters will be used as reference to further characterize any objective tumor regression in the measurable dimension of the disease.

Non-target lesions. All other lesions (or sites of disease) including any measurable lesions over and above the 5 target lesions should be identified as **non-target lesions** and should also be recorded at baseline. Measurements of these lesions are not required, but the presence, absence, or in rare cases unequivocal progression of each should be noted throughout follow-up.

### 12.3 Methods for Evaluation of Measurable Disease

All measurements should be taken and recorded in metric notation using a ruler or calipers. All baseline evaluations should be performed as closely as possible to the beginning of treatment and never more than 4 weeks before the beginning of the treatment.

The same method of assessment and the same technique should be used to characterize each identified and reported lesion at baseline and during follow-up. Imaging-based evaluation is preferred to evaluation by clinical examination unless the lesion(s) being followed cannot be imaged but are assessable by clinical exam.

Clinical lesions: Clinical lesions will only be considered measurable when they are superficial (e.g., skin nodules and palpable lymph nodes) and  $\geq 10$  mm diameter as assessed using calipers (e.g., skin nodules). In the case of skin lesions, documentation by color photography, including a ruler to estimate the size of the lesion, is recommended.

Chest x-ray: Lesions on chest x-ray are acceptable as measurable lesions when they are clearly defined and surrounded by aerated lung. However, CT is preferable.

Conventional CT and MRI: This guideline has defined measurability of lesions on CT scan based on the assumption that CT slice thickness is 5 mm or less. If CT scans have slice thickness greater than 5 mm, the minimum size for a measurable lesion should be twice the slice thickness. MRI is also acceptable in certain situations (e.g. for body scans), but NOT lung.

Use of MRI remains a complex issue. MRI has excellent contrast, spatial, and temporal resolution; however, there are many image acquisition variables involved in MRI, which greatly impact image quality, lesion conspicuity, and measurement. Furthermore, the availability of MRI is variable globally. As with CT, if an MRI is performed, the technical specifications of the scanning sequences used should be optimized for the evaluation of the type and site of disease. Furthermore, as with CT, the modality used at follow-up should be the same as was used at baseline and the lesions should be measured/assessed on the same pulse sequence. It is beyond the scope of the RECIST guidelines to prescribe specific MRI pulse sequence parameters for all scanners, body parts, and diseases. Ideally, the same type of scanner should be used and the image acquisition protocol should be followed as closely as possible to prior scans. Body scans should be performed with breath-hold scanning techniques, if possible.

PET-CT: At present, the low dose or attenuation correction CT portion of a combined PET-CT is not always of optimal diagnostic CT quality for use with RECIST measurements. PET-CT scans are not always done with oral and IV contrast. In addition, the PET portion of the CT introduces additional data which may bias an investigator if it is not routinely or serially performed. For these reasons, we will not allow PET-CT use for RECIST 1.1 response criteria.

Ultrasound: Ultrasound is not useful in assessment of lesion size and should not be used as a method of measurement. Ultrasound examinations cannot be reproduced in their entirety for independent review at a later date and, because they are operator dependent, it cannot be guaranteed that the same technique and measurements will be taken from one assessment to the next.

If new lesions are identified by ultrasound in the course of the study, confirmation by CT or MRI is advised. If there is concern about radiation exposure at CT, MRI may be used instead of CT in selected instances.

Endoscopy, Laparoscopy: The utilization of these techniques for objective tumor evaluation is not advised. However, such techniques may be useful to confirm complete pathological response when biopsies are obtained or to determine relapse in trials where recurrence following complete response (CR) or surgical resection is an endpoint.

Cytology, Histology: These techniques can be used to differentiate between partial responses (PR) and complete responses (CR) in rare cases (e.g., residual lesions in tumor types, such as germ cell tumors, where known residual benign tumors can remain).

*The cytological confirmation of the neoplastic origin of any effusion that appears or worsens during treatment when the measurable tumor has met criteria for response or stable disease is mandatory to differentiate between response or stable disease (an effusion may be a side effect of the treatment) and progressive disease.*

## **12.4 Response Criteria**

### **12.41 Evaluation of Target Lesions**

Complete Response (CR): Disappearance of all target lesions. Any pathological lymph nodes (whether target or non-target) must have reduction in short axis to <10 mm.

Partial Response (PR): At least a 30% decrease in the sum of the diameters of target lesions, taking as reference the baseline sum diameters.

Progressive Disease (PD): At least a 20% increase in the sum of the diameters of target lesions, taking as reference the smallest sum on study (this includes the baseline sum if that is the smallest on study). In addition to the relative increase of 20%, the sum must also demonstrate an absolute increase of at least 5 mm. (Note: the appearance of one or more new lesions is also considered progressions).

Stable Disease (SD): Neither sufficient shrinkage to qualify for PR nor sufficient increase to qualify for PD, taking as reference the smallest sum diameters while on study.

### **12.42 Evaluation of Non-Target Lesions**

Complete Response (CR): Disappearance of all non-target lesions and normalization of tumor marker level. All lymph nodes must be non-pathological in size (<10 mm short axis).

Non-CR/Non-PD: Persistence of one or more non-target lesion(s).

Progressive Disease (PD): Appearance of one or more new lesions and/or *unequivocal progression* of existing non-target lesions. *Unequivocal progression* should not normally trump target lesion status.

It must be representative of overall disease status change, not a single lesion increase.

Although a clear progression of “non-target” lesions only is exceptional, the opinion of the treating physician should prevail in such circumstances, and the progression status should be confirmed at a later time by the review panel (or Principal Investigator).

**12.43 Evaluation of Best Overall Response**

The best overall response is the best response recorded from the start of the treatment until disease progression/recurrence (taking as reference for progressive disease the smallest measurements recorded since the treatment started). The patient's best response assignment will depend on the achievement of both measurement and confirmation criteria.

**For Patients with Measurable Disease (i.e., Target Disease)**

Target Lesions	Non-Target Lesions	New Lesions	Overall Response	Best Overall Response when Confirmation is Required*
CR	CR	No	CR	≥4 wks. Confirmation**
CR	Non-CR/Non-PD	No	PR	≥4 wks. Confirmation**
CR	Not evaluated	No	PR	
PR	Non-CR/Non-PD/not evaluated	No	PR	
SD	Non-CR/Non-PD/not evaluated	No	SD	Documented at least once ≥4 wks. from baseline**
PD	Any	Yes or No	PD	no prior SD, PR or CR
Any	PD***	Yes or No	PD	
Any	Any	Yes	PD	

\* See RECIST 1.1 manuscript for further details on what is evidence of a new lesion.

\*\* Only for non-randomized trials with response as primary endpoint.

\*\*\* In exceptional circumstances, unequivocal progression in non-target lesions may be accepted as disease progression.

Note: Patients with a global deterioration of health status requiring discontinuation of treatment without objective evidence of disease progression at that time should be reported as “*symptomatic deterioration.*” Every effort should be made to document the objective progression even after discontinuation of treatment.

**For Patients with Non-Measurable Disease (i.e., Non-Target Disease)**

Non-Target Lesions	New Lesions	Overall Response
CR	No	CR
Non-CR/non-PD	No	Non-CR/non-PD*
Not all evaluated	No	not evaluated
Unequivocal PD	Yes or No	PD
Any	Yes	PD
* ‘Non-CR/non-PD’ is preferred over ‘stable disease’ for non-target disease since SD is increasingly used as an endpoint for assessment of efficacy in some trials so to assign this category when no lesions can be measured is not advised		

**13.1 CRITERIA FOR REMOVAL FROM STUDY**

Study treatment will be discontinued for the following reasons:

- Progression of disease
- Persistent or unacceptable toxicity despite appropriate dose reductions
- Withdrawal of consent
- If in the opinion of the investigator continuation on study poses unreasonable risks to the patient. This might include patients who fail to return for adequate follow-up, hampering the ability to monitor toxicities

Any patient discontinuing study drug should be seen at 30 days post discontinuation for the evaluations outlined in the study schedule. The patient’s tumor status should be assessed clinically and, if appropriate, disease progression should be confirmed by radiological assessment.

After discontinuation of the study medication at any point in the study, all ongoing AEs or SAEs must be followed until resolution unless, in the investigator's opinion the condition is unlikely to resolve due to the patients underlying disease, or the patient is lost to follow up. All new AEs and SAEs occurring during the 30 calendar days after the last dose of study medication must be reported and followed to resolution as above. Patients should be contacted at least 30 days after discontinuing study medication to collect and /or complete AE information. Any untoward event occurring subsequent to the 30-day follow-up AE reporting period that the investigator assesses as possibly related to the study medication should also be reported as an AE.

Any patient, who has not yet shown objective disease progression, should continue to be followed as per RECIST 1.1.

## 14.1 BIOSTATISTICS

This is a single institution, single-arm unblinded Phase II trial of enzalutamide 160 PO QD in patients with AR (+) ovarian, primary peritoneal, or fallopian tube cancer with measurable disease following 1-3 prior cytotoxic therapies. The primary endpoint includes both the progression free survival (PFS) at 6 months, which detects stabilization of disease, and the best overall response (complete or partial response by RECIST 1.1). If either endpoint indicates efficacy, the treatment will be considered clinically interesting and worthy of further investigation.

## 14.2 Safety Lead-in

In order to reduce patient risk, we will examine in detail the first cycle DLT and other safety data for the first 15 patients before enrolling the rest of the study's patients. A patient is considered toxicity-free for the purpose of the trial if he/she completes the first cycle of therapy (28 days) without experiencing a DLT as defined as:

- And event consistent with a seizure of any grade
- Grade  $\geq 3$  diarrhea, nausea, or vomiting that does not improve to Grade 1 within 14 days of initiating standard of care therapy
- Grade  $\geq 3$  platelet count with associated bleeding
- Grade  $\geq 3$  absolute neutrophil count (ANC) that persists for 7 or more days or that is associated with fevers (febrile neutropenia)
- Any other  $\geq$  Grade 3 non-hematologic toxicity determined to be related to study drug

If a patient experiences a DLT during cycle 1, but is able to continue on protocol following dose holding/dose reduction, they will still be considered a DLT.

Based on Gönen [31], we utilize a Bayesian interpretation for  $\theta$  (the probability of DLT at a planned dose;  $\sim \text{Beta}(\alpha, \beta)$ ). The number of observed DLTs ( $X_s$ ) in the safety lead-in

cohort of  $N_s$  patients is assumed to follow a binomial distribution ( $P(X_s | \theta) \propto \theta^{X_s} (1 - \theta)^{N_s - X_s}$ ). Therefore, the posterior distribution of  $P(\theta | X_s)$  is  $\text{Beta}(\alpha + X_s, \beta + N_s - X_s)$ . A uniform prior as

$Beta(\alpha=1, \beta =1)$  is used to reflect the uncertainty value for  $\theta$  as suggested by Gönen [31].

Let  $N_s =15$ , the probability that  $\theta$  exceeds various targets (i.e. 0.2, 0.3, 0.4) given the observed DLT patients' number ( $P(\theta|X_s)$ ) can be calculated. They are listed in the following table:

DLT # in the 15 safety lead-in patients	$P(\theta>0.2)$	$P(\theta>0.3)$	$P(\theta>0.4)$
0	0.028	0.003	0.000
1	0.141	0.026	0.003
2	0.352	0.099	0.018
3	0.598	0.246	0.065
4	0.798	0.450	0.167
5	0.918	0.660	0.329
6	0.973	0.825	0.527
7	0.993	0.926	0.716
8	0.999	0.974	0.858
9	1.000	0.993	0.942
10	1.000	0.998	0.981
11	1.000	1.000	0.995
12	1.000	1.000	0.999
$\geq 13$	1.000	1.000	1.000

Based on the table above, if we observe 0/15 patients with DLTs in the safety lead-in cohort, there is 0.003 chance that  $\theta$  exceeds 0.3; whereas, if 5/15 patients with DLTs are observed, the chance that  $\theta$  exceeds 0.3 increases to 0.660. Given these probabilities at the end of safety lead-in, we can make informed decisions regarding the appropriateness of the choice of the following trial (i.e. if  $\geq 5$  DLTs observed in the safety lead-in cohort, the trial will be halted immediately and the PI will examine the toxicity profile and determine whether lower doses will be added).

#### 14.2. Sample size calculation for the two-stage phase II trial

Prior targeted therapies for treatment of ovarian, primary peritoneal, and fallopian tube cancer have shown response rates of 0%-21% and PFS at 6 months of 6.5%-40.3% in patients with recurrent or advanced ovarian, primary peritoneal, or fallopian tube cancer and a history of 1-2 prior cytotoxic therapies. We hypothesize that treatment with enzalutamide will result in an increase in tumor response rate from 5% to 20% or an increase in 6-month PFS rate from 15% to 30% ( $H_0: \pi_r \leq 0.05$  and  $\pi_{pfs} \leq 0.15$  vs.  $H_1: \pi_r > 0.05$  or  $\pi_{pfs} > 0.15$ ). To test the null hypotheses in a two-stage design, a method provided by Sill and Yothers [32] is used. In particular, in stage I, 28 eligible patients will be evaluated, if 3 or more patients have clinical response or 5 or more patients have no progression/death at 6 months, then the study will open to the second stage accrual. In

stage II, an additional 31 patients will be enrolled. At the end of stage II, if at least 7 of 59 (28+31=59) patients have clinical response or at least 13 of 59 patients survive progression free for 6 months, this will be considered as a positive trial.

Assuming the two primary endpoints are independent, the power in each scenario and the type 1 error are listed as in the following table:

		PFS rate at 6mo	
		$\pi_{pfs} = 0.3$	$\pi_{pfs} = 0.15$
Response	$\pi_{rr} = 0.20$	0.99	0.94
	$\pi_{rr} = 0.05$	0.90	0.10

Assuming the two primary endpoints are highly correlated (as the joint probability of  $\pi_{rr}$  and  $\pi_{pfs}$  is  $0.90 \times \min(\pi_{rr}, \pi_{pfs})$  [32]), the power in each scenario and the type 1 error are as the following:

		PFS rate at 6mo	
		$\pi_{pfs} = 0.3$	$\pi_{pfs} = 0.15$
Response	$\pi_{rr} = 0.20$	0.97	0.92
	$\pi_{rr} = 0.05$	0.90	0.09

When the null hypotheses are true for both the response and the PFS, the chance of stopping the trial after stage I enrollment is 49% under independence and 55% under dependence.

The clinical response and the PFS from the starting of the treatment will be documented for each patient (including the patients in the safety lead-in). All the patients enrolled in this phase will be included in the main analysis of response and PFS. Patients who are lost to follow-up within 6 months are considered as failures for the PFS binary outcome of PFS within 6 months: yes/no. The response rate will be calculated. The patients accrued during the safety lead-in period will be included in the first stage of two-stage phase II portion. With the accrual rate of 3-6 patients per months, accrual of the 28 stage I patients should be complete within 9 months. After confirming promising results from stage I, the accrual of an additional 30 stage II patients should be complete within 10 months. The expected total trial duration is 30 months.

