If  $< 5$  patients develop one of the above events during the first 28 days of treatment then enrollment will proceed following a two-stage design. A total of 28 patients (including the first 15) will be enrolled during the first stage. If 3 or more patients have clinical response or 5 or more patients have no progression/death at 6 months, then the study will open to the second stage of accrual. No more than 9 out of the 28 patients (1/3) enrolled during stage I will have 3 prior therapies. In stage II, an additional 30 patients will be enrolled. At the end of stage II, if at least 7 of 59 (28+30=58) patients have clinical response or at least 13 of 59 patients survive progression free for 6 months, this will be considered as a positive trial.

Patients will be evaluated for radiographic response every 2 cycles (8 weeks) and at the end of study. Response is defined as the best over-all response achieved by RECIST 1.1 criteria while on study treatment.

At end of treatment an optional tumor biopsy will be performed in patients who consent to this procedure.

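### Stage II is given as both 31 patients (total 59) and 30 patients (total 58), and the printed power and type I error tables belong to 58, not 59

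*Combined protocol and SAP*

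**What the plan says.** The stage II size and the final total appear in three places in the current text.

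- **Section 14.2, Sample size calculation:** "stage II, an additional 31 patients will be enrolled", and the trial is positive "if at least 7 of 59 (28+31=59) patients have clinical response or at least 13 of 59 patients survive progression free for 6 months". The two tables of power and type I error follow directly, so they read as properties of a 59-patient design.
- **Section 14.2, accrual paragraph after the tables:** "the accrual of an additional 30 stage II patients should be complete within 10 months". No total is printed there, but 28 + 30 = 58.
- **Section 4.3:** "In stage II, an additional 30 patients will be enrolled", and then the decision rule "if at least 7 of 59 (28+30=58) patients have clinical response or at least 13 of 59 patients survive progression free for 6 months". The denominator is 59 while the sum in the brackets is 58.

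The final cut-offs, 7 responses or 13 patients progression-free at 6 months, are the same in Sections 4.3 and 14.2. So are the stage I size of 28 and the continuation rule.

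**The concern.** In a single-arm two-stage design, the total sample size, the final cut-offs and the error rates form one package. Moving one patient with the cut-offs fixed changes the error rates. Here the text gives two totals and one set of tables, so at most one total can be the one the tables were computed for.

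Two things are at stake. First, study staff need to know whether accrual closes at 58 or 59, and the analyst needs to know the denominator of the primary decision rule. Second, if the tables were computed for 58 and the trial enrols 59 under the same cut-offs, Section 14.2 understates the type I error of the design it describes.

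**Working it through.** **Inputs, all from Section 14.2 (Sample size calculation).**

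- Response rate: 0.05 under the null, 0.20 under the alternative. Six-month PFS rate: 0.15 and 0.30.
- Continuation rule: "28 eligible patients will be evaluated, if 3 or more patients have clinical response or 5 or more patients have no progression/death at 6 months". Meeting either condition lets the trial go on.
- Final rule: positive if the trial continued and total responses are at least 7 or total progression-free patients at least 13.
- Joint probability that one patient has both outcomes: the product of the two rates (independent), or 0.90 times the smaller rate (correlated).

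**Method.** Each patient falls into one of four cells (both outcomes, response only, progression-free only, neither). Let (R1, P1) be the stage I counts in 28 patients and (R2, P2) the counts in n2 stage II patients. The exact probability of a positive trial is

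P(positive) = Σ P(R1, P1) × P(R1 + R2 ≥ 7 or P1 + P2 ≥ 13), summed over all (R1, P1) with R1 ≥ 3 or P1 ≥ 5.

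**Step 1: reproduce a figure that does not depend on stage II.** The plan states that "the chance of stopping the trial after stage I enrollment is 49% under independence and 55% under dependence". Under independence and the null:

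- P(R1 ≤ 2), Binomial(28, 0.05) = 0.8373
- P(P1 ≤ 4), Binomial(28, 0.15) = 0.5869
- Product = 0.4915, which matches 49%

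In the correlated case the joint enumeration gives 0.5481, which matches 55%. The stage I rule and both correlation assumptions are therefore read as the plan intended.

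**Step 2: compute the tables at each total.**

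| Endpoints | Response, PFS | Printed | N = 58 (n2 = 30) | N = 59 (n2 = 31) |
|---|---|---|---|---|
| Independent | 0.20, 0.30 | 0.99 | 0.9945 | 0.9951 |
| Independent | 0.20, 0.15 | 0.94 | 0.9385 | 0.9421 |
| Independent | 0.05, 0.30 | 0.90 | 0.9050 | 0.9137 |
| Independent | 0.05, 0.15 (null) | 0.10 | 0.0992 | 0.1086 |
| Correlated | 0.20, 0.30 | 0.97 | 0.9669 | 0.9693 |
| Correlated | 0.20, 0.15 | 0.92 | 0.9179 | 0.9209 |
| Correlated | 0.05, 0.30 | 0.90 | 0.9002 | 0.9087 |
| Correlated | 0.05, 0.15 (null) | 0.09 | 0.0904 | 0.0988 |

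- **At 58:** seven of eight cells round to the printed value. The exception is 0.90503, which rounds to 0.91 and is printed as 0.90. The largest gap from print is 0.0050.
- **At 59:** three of eight agree. The five that differ are 1.00 against 0.99, 0.91 against 0.90 (twice), 0.11 against 0.10, and 0.10 against 0.09. The largest gap is 0.91375 − 0.90 = 0.0137.

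**Step 3: could another reading make 59 fit?**

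- *Other totals, same cut-offs.* For totals 55, 56, 57, 58, 59, 60 and 61, the number of matching cells is 1, 1, 1, 7, 3, 2 and 1. Only 58 fits closely.
- *Truncation instead of rounding at 59.* Six of eight cells would match. But 0.91375 cannot become 0.90 either way, and 0.96934 would truncate to 0.96 against a printed 0.97.
- *An endpoint counts at the end only if it passed its own stage I cut-off, at 59.* Type I error is 0.105 and 0.097, and the cell printed as 0.94 becomes 0.927.
- *Cut-offs read as strictly greater than, at 59.* Type I error is 0.048 (independent) and early stopping 73%, far from the printed 0.10 and 49%.
- *Excusing both near-boundary cells* (0.90503 at 58 and 0.99514 at 59). Mismatches are then 0 at 58 and 4 at 59.

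**The case against.** The strongest reply is that this is one patient and under one percentage point. Section 14.2 declares no limit on alpha: 0.10 and 0.09 are computed properties, so 0.109 breaches nothing. At 59 no power falls below its printed value. The stage I rule and the stopping probabilities do not move. The cut-offs of 7 and 13 are counts that can be applied at either total, so the conclusion could change only if the 59th patient alone moved a count from 6 to 7 or from 12 to 13 while the other endpoint had not met its cut-off. The evidence from the tables also rests on second-decimal differences, one of the five mismatches at 59 is itself near a rounding boundary, and 58 does not reproduce the print perfectly. Power alone does not separate the two totals well.

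All of this is fair as to size. It does not remove the contradiction. The stage II size is stated both ways in running text, and one sentence of Section 4.3 carries both totals. Nor does it explain the tables: both type I errors agree with print at 58 and neither does at 59, and no other reading tried brings 59 into line.

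**Conclusion.** The concern holds: the plan is wrong as written. The stage II size is 31 in one paragraph of Section 14.2 and 30 in another. Section 4.3 plans 30 but divides by 59. The printed tables are those of a 58-patient design, apart from one cell at a rounding boundary.

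If 59 patients are enrolled with unchanged cut-offs, type I error is 0.109 (independent) and 0.099 (correlated), against the printed 0.10 and 0.09. That is an increase over print of 0.1086 − 0.10 = 0.0086 and 0.0988 − 0.09 = 0.0088. Power is at or above print throughout. The numerical consequence is small. The reason to correct it is that the sample size and the denominator of the primary decision rule must be unambiguous and must match the error rates quoted for them.

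The result assumes the decision rules exactly as stated in Section 14.2 and its two joint-probability models. The match to the 49% and 55% stopping figures supports that reading.

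**What to change.** Choose one total and carry it through Sections 4.3 and 14.2, before the final analysis.

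- **Option (a), 30 and 58.** In Section 14.2 change stage II to 30 and the sum to 28 + 30 = 58. In Sections 4.3 and 14.2 change the denominators so that the cut-offs read 7 of 58 and 13 of 58. Keep the tables after checking the independent cell for response 0.05 and PFS 0.30 (0.90503, which rounds to 0.91). The accrual paragraph already agrees.
- **Option (b), 31 and 59.** Change stage II to 31 in Section 4.3 (with the sum 28 + 31 = 59) and in the accrual paragraph. Restate type I error as 0.11 (independent) and 0.10 (correlated). Restate power, in the row order used above, as 1.00 / 0.94 / 0.91 (independent) and 0.97 / 0.92 / 0.91 (correlated).

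Option (a) is a wording amendment with no added patients, and it agrees with the accrual paragraph, the Section 4.3 sum and the tables. Option (b) adds one patient to the number given in Section 4.3 and the accrual paragraph, and it changes five of the eight stated operating characteristics. The cut-offs and the stage I rule stay as they are under both.
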